Background information: The proposed 3-year adaptation and pilot testing of the Asian Women’s Action for Resilience and Empowerment (AWARE): A Stage IA and IB Intervention Development Study consists of the following goals: (1) provide the original Seeking Safety (SS) ¹ curriculum to Asian Women Discussion Group members for feedback and revision; (2) fully develop the AWARE protocol (which will modify SS by integrating Project FIO² and our cultural component) for API women; (3) use a pilot two-armed RCT design to test the feasibility and safety of our adapted intervention in Year 2, comparing the AWARE intervention group (n=48) with the wait-list group (n =48); and (4) employ multiple measures of the same constructs using a repeated measures design (assessments at pre-test, 8 weeks, and 3-month follow-up). We chose an RCT design to (1) establish the validity of statistical testing to the maximum level and (2) minimize potential biases (known and unknown factors and characteristics of the intervention and control groups). We will obtain outcomes for feasibility, safety, and preliminary efficacy of the primary outcomes (HIV-related outcomes) and secondary outcomes (psychiatric symptoms, substance use). These feasibility, safety, and efficacy outcomes will allow us to better plan for a larger-powered study. We will conduct the focus groups and pilot RCT at Boston University, School of Social Work (BUSSW), MA.

Study rationale and significance: *There is a mental and sexual health crisis in the API community in the US, particularly among young women (ages 18-35). This proposed*

project is intended to deepen our national understanding of this crisis and move us toward highly innovative solutions. We propose to design an appropriate intervention that reduces mental and sexual health problems in this population. There are 3 significant reasons why this study should be funded for research:

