3. Low reporting rates and under-utilization of treatment for traumatized API women. API women who were victims of sexual assault are particularly vulnerable. API women may experience higher levels of psychological distress or have fewer adaptive coping skills/social supports compared to sexually-victimized White women.³³ Rau and Diclemente found that API parents of sexual victims provide less support and minimal involvement in helping victims to seek evaluation and treatment with the appropriate services.³⁷ Our AWWHIP study showed that the experience of child sexual abuse combined with other types of abuse was the most powerful and robust predictor of severe depression, suicidal ideation, and suicide attempts.²⁶

Study objectives and/or hypotheses: The aim for *year one* is to adapt an intervention for API women that reduces HIV risk behaviors while increasing HIV knowledge and self-efficacy in negotiating safer sex (primary outcomes) and reduces psychiatric symptom severity and substance use (secondary outcomes). During *year 2*, the feasibility and safety of stage 1B of the AWARE intervention will be established through a pilot RCT, in which an intervention group will receive AWARE (n=48), which will have adapted SS by integrating Project FIO and

cultural components. During *years 2 and 3*, the preliminary efficacy of the intervention for API women will be tested.

It is hypothesized that the AWARE intervention group will significantly exceed the wait-list group in reduction of HIV risk behaviors and increased HIV knowledge and self-efficacy in negotiating safer sex at the 8 weeks and 3 months post-test points (primary outcomes). Additionally, the AWARE intervention group will significantly exceed the wait-list group in reduction of PTSD symptoms (and/or other mental health outcomes) and the frequency of substance use (at 8 weeks and 3 months post-test) (secondary outcomes).

Section E: Study subjects

E. 1. Gender

Select gender of subjects: ___ male female ___ both

E. 2. Age

Age range of subjects: (check all categories that apply to any of the subjects)

- Adults (18 years and older)
 Infants (< 1 year)
 Young children (1-6 years of age)
 Children 7-11 years
 Adolescents (12-17 years of age)

E. 3. Race/ Ethnicity (check all that apply)

- Mixed race or ethnicity
 American Indian or Alaskan Native
 Asian or Pacific Islander
 Black (not of Hispanic Origin)
 Hispanic
 White (not of Hispanic Origin)

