a. Self-mutilation: We will assess self-mutilation using the Columbia-Suicide Severity Rating Scale (C-SSRS). The C-SSRS is a scale administered by a trained individual to assess past suicide attempts and severity of suicidality. Questions address suicidal ideation, intensity of ideation, non-suicidal self-injury, and actual suicide attempts. Questions have either yes/no answers or answer choices scored on a severity of 1-5. The scale exhibits a moderate to high internal consistency, with Cronbach's alpha of 0.7, 0.7, and 0.9, respectively for three existing studies.

b. Suicidality: We will also assess suicidality using the C-SSRS (see item a, above).

c. Intimate Partner Violence (IPV): We will assess IPV using the Revised Conflict Tactics Scale (CTS2). The CTS2 is a self-administered questionnaire which measures the extent of partner conflict and negotiation tactics used. A scale of 0 to 7 to rate 78 relationship behaviors based on frequency. The items belong to the following categories: Negotiation, Psychological Aggression, Physical Assault, Sexual Coercion, and Injury. Cronbach's alpha coefficients range from 0.86- 0.95. Those who meet the criteria severe IPV will be excluded. Women who report 1 or higher (i.e., "My partner did this to me one or more times") for any items in the "Severe" subscale of the Physical Assault, Sexual Coercion, and Injury scales will be excluded from the study (these items are bolded and highlighted on the CTS2, enclosed). Examples of "severe" items include "My partner slammed me against a wall" and "My partner beat me up." We will provide appropriate referral sources for additional preventive and clinical services for women who meet criteria for severe IPV at any time during the intervention.

If a participant is determined to be at serious risk for suicidal ideation, suicide attempts, self-mutilation, or severe IPV at any assessment point (clinical screening, baseline, 8 weeks, and 3-month follow-up), or through the Adverse Event Log, weekly contact, wait-list group follow-up (at 3 weeks and 6 weeks after randomization), or text messaging, the therapist will call [name] immediately by telephone. [name] will then call the participant and immediately assess suicide risk. If risk is determined to be present, the following protocol will be implemented depending on level of risk:

(1) Mild risk (e.g. suicidal ideation present without presence of current plan, low intent, presence of hope, no current means).

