In Year 1 (the intervention development phase), we will begin recruiting and screening participants from AWARE. The first 10 women who pass the eligibility screenings and agree to participate the study will be invited to participate as members of the Asian Women Discussion Group, which will serve as a focus group. Although we will administer our preliminary AWARE intervention to the ten selected participants, there is no experimental intervention for the Asian Women Discussion Group. The sole purpose of this focus group is for members to give feedback from the perspective of AWARE intervention participants (as both the Asian Women Discussion Group and the AWARE group must meet the same demographic and clinical criteria). Members in this focus group will be ineligible to participate in the AWARE intervention group (Phase 2 of the study). Members in the Asian Women Discussion Group will attend 10 psychotherapy sessions and an additional discussion meeting afterward, as well as an additional session in September.

2) *AWARE intervention group*

In Year 2 of our study, using Asian Women Discussion Group’s feedback and other revisions made during the intervention development phase (in Year 1), we will administer our improved AWARE intervention (Stage IB) to 48 randomly-selected eligible participants. Participants in this group will receive 8 consecutive weekly sessions to receive the manualized intervention. After the last session, participants will be scheduled to return for a 3-month follow-up.

3) *Wait-list (or, delayed treatment) group*

Also in Year 2, the wait-list group will receive the exact same intervention 3 months *after* the start of the AWARE intervention group. The wait-list group will be comprised of 48 randomly-selected eligible participants.

Detailed Procedure:

1. In Year 1, for recruitment of Asian Women Discussion Group participants, we will use first use the database of 720 women who participated in the PI’s prior study (AWSHIP).

We will randomly select approximately 100 AWWSHIP women (who previously indicated interest in future studies) and ask them to participate in the initial eligibility screening. The function and purpose of Asian Women Discussion Group will be described to each woman by phone, letter, or email.

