6. In Year 2, we will recommence our recruitment efforts to identify and enroll eligible women into the intervention group and the wait-list group. The interviews during the screening process will be audio-recorded. Women who will be screened in Year 2 go through the same process as women who screened in Year 1 for Asian Women Discussion Group and must meet the same eligibility requirements (see Step 2 and Step 3).
7. Our goal is to screen about 400 women in Year 2. Of this number, we expect about 30% (n=120) to meet all eligibility criteria. We will randomly select 96 eligible women and assign 48 to the AWARE intervention group and 48 to the wait-list group.
8. Individual participation in the AWARE intervention group includes:
 - a. Written consent to participate including consent for the audiotaping of each session.
 - b. Completion of a baseline assessment prior to the start of the group sessions.
 - c. Participation in 105-minute group sessions each week (for a total of 8 weeks) with a small group of other participants and a clinician, covering topics including: Safety, Taking Good Care of Yourself, Compassion, Commitment, Creating Meaning, Setting Boundaries in Relationships, Coping with Triggers, Healthy Relationships, Self-Nurturing, and The Life Choices Game
 - d. \$26 payment and \$4 transportation reimbursement for each weekly group session and \$20 payment and \$4 transportation reimbursement for each assessment.
 - e. Completion of a weekly Adverse Events Log and a weekly questionnaire on the AWARE stories.
 - f. Receipt of and response to daily, secure mobile text messages (called “AWARE Stories”) in between each weekly session to reinforce participation and adherence
 - g. Completion of assessments upon the last intervention session
 - h. Completion of outcome assessments in a follow-up visit 3 months after the last intervention session
9. Individual participation in the wait-list group includes:
 - a. Written consent to participate including consent for the audiotaping of each session.
 - b. Completion of a baseline assessment prior to the start of the group sessions.
 - c. Participation in 90-minute group sessions each week (for a total of 8 weeks plus an additional post-intervention meeting) with a small group of other participants and a clinician, covering topics including: Safety, Taking Good Care of Yourself, Compassion, Commitment, Creating Meaning, Setting Boundaries in Relationships,

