Coping with Triggers, Healthy Relationships, Self-Nurturing, and The Life Choices Game

- d. \$26 payment and \$4 transportation reimbursement for each focus group session and \$20 payment and \$4 transportation reimbursement for each assessment.
- e. Completion of a weekly Adverse Events Log and a weekly questionnaire on the AWARE stories.
- f. Receipt of and response to daily, secure mobile text messages (called “AWARE Stories”) in between each weekly session to reinforce participation and adherence.
- g. Completion of assessments upon the last intervention session.
- h. Completion of outcome assessments in a follow-up visit 3 months after the last intervention session.

F.5. Primary outcomes

Indicate in the box below anticipated primary and secondary outcomes if applicable

Primary outcomes: decrease in HIV risk behaviors, increase in HIV knowledge, increase in self-efficacy in negotiating safer sex

Secondary outcomes: decreased psychiatric symptom severity and decreased substance use

F.6. Surveys, interviews, questionnaires, etc.

You must attach to this application all surveys, interviews, questionnaires, focus group outlines, etc. that will be used in this study. The IRB must review these materials as part of its review.

Failure to provide this information could result in a delay in IRB review. If some of the materials are not finalized- submit the DRAFT versions. The final versions will need to be approved by the IRB via an amendment PRIOR to use.

I have attached all surveys, interviews, questionnaires, data collection forms that will be used in this study

Section G: Sample Size /Data Analysis

G. 1. Sample Size

Indicate in the box below how many subjects you anticipate will be enrolled in this study (or how many records you will review). If this protocol involves more than one cohort or study phase please specify anticipated sample size for each cohort /study phase. If this study involves multiple experiments you may attach a table summarizing anticipated enrollments by experiment and subject category.

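### The protocol contradicts itself on when wait-list women are assessed: step 9 of F.4 omits the untreated week-8 assessment that the hypotheses and models need

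*Protocol*

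**What the plan says.** The general statements describe one schedule for both arms. Section D, Background information, gives the repeated-measures design as "assessments at pre-test, 8 weeks, and 3-month follow-up". Section D, Study objectives, places the primary between-arm hypothesis at the same points: "self-efficacy in negotiating safer sex at the 8 weeks and 3 months post-test points (primary outcomes". The study summary in Section C, the adverse-event text in E.5.B, the adherence comparison and efficacy models in G.3, and the payment list in L.2 all refer to an 8-week assessment as well. G.1 says that the control group receives no treatment.

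The procedures in F.4 read differently. Item 3 of the overview says "the wait-list group will receive the exact same intervention 3 months" after the AWARE arm starts. Step 9 then sets out participation for the wait-list arm:

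- 9(b): "Completion of a baseline assessment prior to the start of the group sessions", without saying whose sessions or how far ahead
- 9(c): sessions "for a total of 8 weeks plus an additional post-intervention meeting"
- 9(g): "Completion of assessments upon the last intervention session"
- 9(h): "Completion of outcome assessments in a follow-up visit 3 months after the last intervention session"

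The assessment items repeat those of step 8 for the AWARE arm. For the waiting period, the only contacts stated specifically for this arm are two telephone checks for adverse events. E.5.B counts these once from the start of AWARE treatment and once as "wait-list group follow-up (at 3 weeks and 6 weeks after randomization".

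**The concern.** A wait-list design yields a treatment effect only from values taken while the control arm is still waiting. Step 9 ties both post-baseline assessments to the arm's own delayed sessions and names none during the wait. Staff working from the procedure section could therefore complete every listed visit and never measure an untreated control woman after baseline. A group-by-time model on visits labelled post and 3-month would then estimate immediate against delayed AWARE, and a real effect would largely cancel. An analysis plan cannot repair this, because a measurement that was not taken at week 8 cannot be recovered.

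**Working it through.** **Inputs.** The delay to wait-list treatment is 3 months (F.4, overview item 3), and there are 8 weekly sessions in each arm (F.4, overview and steps 8 and 9). Each arm's follow-up is 3 months after its last session (8h and 9h). There are 48 women per arm, with 15% dropout by week 8 (G.3). I take AWARE's first session as week 0 and 3 months as 12 to 13 weeks. The eighth weekly session falls 7 weeks after the first and is counted as 7 to 8.

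**Timeline under steps 8 and 9 read literally.**

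| | AWARE | Wait-list |
|---|---|---|
| First session | week 0 | week 12-13 |
| Baseline | about week 0 | about week 0, or up to week 12-13 (9b is silent) |
| Last-session assessment | week 7-8 | 12 + 7 = 19 to 13 + 8 = 21 |
| 3-month follow-up | 7 + 12 = 19 to 8 + 13 = 21 | 19 + 12 = 31 to 21 + 13 = 34 |

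Step 9 lists no wait-list outcome assessment between the start of that arm's sessions and about week 19. It lists none before those sessions other than the undated baseline.

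**Expected contrast by nominal visit.** Let the effect of the eight sessions on change from baseline be d in each arm, with the same background trend s. Under step 9 the expected difference at the post visit is (s + d) - (s + d) = 0, whatever d is. The same holds at the 3-month visit. With an untreated week-8 control it is (s + d) - s = d.

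**Illustration.** The protocol gives no effect size, standard deviation or power, so there is no planned figure to reproduce. I assume standardized effects of 0.3 to 0.8 and a two-sided level of 0.05. The number per arm is n = 48 x 0.85 = 40.8, and the standard error is sqrt(2/40.8) = 0.221. Power is about Phi(d/0.221 - 1.96).

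| Assumed d | Power with an untreated week-8 control |
|---|---|
| 0.3 | 27% |
| 0.5 | 62% |
| 0.6 | 77% |
| 0.8 | 95% |

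If both arms are measured after the same sessions, the contrast is 0 and the rejection rate is the nominal 5%. If half of a 0.6 contrast survived (0.3), power would be 27%.

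**Common trial clock.** If every assessment is counted from AWARE's start, wait-list women are untreated at week 8 and that comparison is sound. The 3-month comparison is not. AWARE's follow-up under 8(h) falls at weeks 19-21, when wait-list women have had most or all of their own sessions. They would still be untreated only if 3 months were counted from baseline, which 8(h) contradicts.

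**Payments.** L.2 names two evaluations after baseline, at 8 weeks and at 3 months. Step 9 already lists two. An untreated week-8 visit plus both step 9 visits makes three, which L.2 does not cover. Step 9(d) pays per assessment without saying how many.

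**The case against.** A reader might infer from step 9 that the trial plans to collect no untreated control value at week 8, and that every wait-list assessment follows treatment. The documents do not support that reading, for four reasons.

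- Sections C, D, E.5.B and G.3 state an 8-week assessment for the two-arm trial, and G.1 describes an untreated control.
- Step 9 is not exhaustive. It introduces its items as things that participation includes, and it leaves out the two telephone checks that E.5.B requires of this arm. Its silence on week 8 is therefore weak evidence that no visit is meant.
- E.5.B presents those checks as additional to the common assessments, and in one place counts them from AWARE's start. That points towards a shared clock.
- 9(b) leaves the baseline undated, so it may well be taken at randomization.

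The close repetition of step 8 makes a drafting carry-over a plausible explanation.

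All of this stands, and it makes the defect a contradiction within the protocol. It does not remove the defect. In the general statements, 8 weeks can also mean the end of each arm's own eight sessions, which is how 9(g) puts it into practice. No passage says that wait-list women attend an outcome visit while waiting. The zero expected difference is also conditional: it needs the literal reading of step 9, equal effects in both arms, and alignment by nominal visit.

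**Conclusion.** The protocol gives two incompatible accounts of the wait-list assessments, and this must be resolved before the randomized stage starts. Under the general statements, the week-8 comparison is valid. Under step 9 taken literally, the arm has no untreated post-baseline outcome value, and both hypothesized comparisons set treated against treated women. The expected difference by nominal visit is then near 0 if the effect is equal in both arms.

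The 3-month hypothesis has no untreated comparator under either account, given 8(h).

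The week ranges assume 12 to 13 weeks for 3 months and 8 weekly sessions. G.1 speaks of 10 sessions; two further weekly sessions would move the post-session dates by two weeks and leave the conclusion unchanged. If the extra meeting in 9(c) counts as the last session, the wait-list dates move later still. The power figures rest on assumed effects and only illustrate what is lost. The two clocks for the week-3 and week-6 calls are a separate, minor inconsistency.

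**What to change.** 1. Rewrite step 9 so that the wait-list baseline and week-8 outcome assessments are timed from the AWARE arm's start (or from randomization), and state that both precede any wait-list session.
2. Limit the randomized efficacy comparison to time points before the wait-list arm starts treatment, with week 8 as the main one.
3. Label assessments after the wait-list arm's own sessions as delayed-treatment data, outside that comparison.
4. Define the origin of 3 months. Restate the 3-month hypothesis in Section D as immediate versus delayed treatment, or drop it as a comparison with untreated controls.
5. State the week-3 and week-6 calls on one clock throughout.
6. Reconcile Section D (background and hypotheses), E.5.B, F.4 (overview item 3, steps 8 and 9), G.1, G.3 and L.2 with the result. This includes the description of the control in G.1 and the number of paid evaluations in L.2.

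The cost is protocol wording. If the week-8 visit is added to the step 9 visits, participant payments rise by at most (20 + 4) x 48 = $1,152. If it replaces a later wait-list visit, they do not rise.

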The participants for the intervention program, Asian Women's Action for Resilience and Empowerment (AWARE) will be comprised of 106 women in total: 10 in the Asian Women Discussion focus group, 48 in the intervention group, and 48 in the wait-list group. The 10 women in Asian Women Discussion Group will participate in the focus group prior to the pilot randomized clinical trial (RCT). We will launch the AWARE campaign to reach out to API women in the greater Boston area and enroll eligible women in our study, using a two-armed randomized design: (1) a group that will receive the 10-session AWARE intervention (n=48) and (2) a wait-list control group who will receive no treatment (n =48). In order to successfully recruit the 96 AWARE participants, we estimate screening 500 women in the community.

G. 2. Sample size justification

Indicate why you chose the sample size proposed. Provide your sample size calculations. If this is a pilot study, this justification does not necessarily require a formal sample size calculation, but should provide a rationale for choosing the sample size proposed (e.g. to estimate a mean to a certain accuracy, to determine if the response rate is above a certain percentage, etc.) **Note: Once the IRB approves a certain study sample size then you may not enroll beyond that sample size without first obtaining approval from the IRB. ****** In determining your sample size be sure to allow for screen failures and study drop-outs in your calculations. Explain how many evaluable subjects you will need to end up with to answer your study question and how many subjects you will need to enroll and consent to achieve this number. The IRB counts study subjects a being enrolled once they have consented.

Our study is a pilot study which does not require a formal sample size calculation.

G. 3. Data Analysis

Provide a description of your plan for data analysis.

- State the types of comparisons you plan (e.g. comparison of means, comparison of proportions, regressions, analysis of variance).
- Which is the PRIMARY comparison/analysis?
- How will the analyses proposed relate to the primary purposes of your study?
- If you are doing qualitative research please state how comparisons will be made.

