Quantitative data for protocol evaluation and participant psychometric monitoring: We will evaluate participants in the Asian Women Discussion Group by comparing the results of pre-intervention and post-intervention psychometric measures. These comparisons will be used to determine if the current protocol is achieving the intervention's goals of providing benefits to participant's mental and behavioral health.

Data Analysis for Aim 2 (year 2):

(1) Feasibility Analysis of group psychotherapy: We conservatively anticipate that 15% of participants will dropout during the 8 week RCT. We also anticipate that another 5% will dropout at the 3-month follow-up evaluation. The first stage of analysis will involve estimating the proportion of women who are eligible and agree to enroll in the study. A 95% confidence interval for the proportion will also be produced. Then, among those who enroll, baseline characteristics will be compared between those randomized to the intervention and those randomized to the wait-list control group to assess balance.

We will estimate the proportion of women who adhere at 8 weeks and 3-month follow-up. Mean proportion of women who attend (at 8 weeks and 3-month follow-up) and 95% confidence intervals will be generated for the total sample and then by groups. We will test the

difference between the participants' adherence rates in the intervention and control group at 8 weeks and 3-month follow-up using a chi-square test. We will then examine bivariate associations between baseline characteristics and attrition (each time point considered separately) using chi-square tests for categorical variables and two sample t tests for continuous variables among all participants. Multivariable associations will be examined using multiple logistic regression models for adherence by group, relating those characteristics that were significant in bivariate analysis to attrition, if sample size permits.

(2) Feasibility Analysis of AWARE Stories (Hypothesis for secure mobile messaging): Higher level of satisfaction and higher utilization of secure text messages are positively associated with group psychotherapy attendance. Ordinal chi-square tests will be used to examine the association between ordinal scale (1-4) of messaging satisfaction and utilization questions and psychotherapy attendance.]

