Evaluation of Pilot RCT Analysis: We will use an intention-to-treat (ITT) analysis, which indicates all women who are randomized will be included for analysis. To test the success of the randomization, prognostic factors including baseline education, psychiatric diagnosis severity, and substance use will be compared between participants in the intervention group and wait-list group using chi-square tests. Baseline characteristics that show imbalance between groups will be adjusted in multivariate regression models. The efficacy outcome variables will be analyzed as either dichotomized or continuous variables. For PTSD, continuous measures of the CAPS will be assessed. In order to sensitively capture any changes in PTSD scores, continuous measure will be chosen. For HIV outcomes, we will use both dichotomous and continuous variables to measure status and severity of the outcomes at baseline, 8 weeks, and 3-month post-test. Mixed effects models will be used to compare the pattern of change in dichotomous and continuous outcomes over time between groups using normal and logit links, respectively. We will first use an unstructured covariance matrix to

account for correlation between repeated measurements in the same participant and compare it to other covariance structures, using goodness of fit. The most suitable covariance matrix will be chosen for the final model. The same approach will be followed for secondary outcomes. All statistical testing will be performed at the significance level of 0.05 using SAS 9.3.102. Additionally, in order to explore whether compliance affects outcome measures, we will compare the sexual risk behavior, psychiatric severity, and substance use measures between those who drop out versus those who complete the intervention using two-tailed, independent samples t-tests.

Data analysis for Aim 3 (year 2 and 3):

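### Baseline predictors of drop-out must pass a 0.05 screen, on about 14 to 19 drop-outs, to enter a model: modest real predictors are mostly missed, and those that pass are overstated

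*Protocol*

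**What the plan says.** Section G.3, Aim 2, part (1) gives the expected losses: "We conservatively anticipate that 15% of participants will dropout during the 8 week RCT", and "We also anticipate that another 5% will dropout at the 3-month follow-up evaluation". It then examines "bivariate associations between baseline characteristics and attrition (each time point considered separately"), using chi-square tests for categorical variables and two-sample t tests for continuous ones, with both arms pooled.

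The next step is multiple logistic regression for adherence by group, "relating those characteristics that were significant in bivariate analysis to attrition, if sample size permits". The level comes from Evaluation of Pilot RCT Analysis in the same section: "All statistical testing will be performed at the significance level of 0.05 using SAS 9.3.102".

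The number of characteristics is not stated, and no threshold defines when the sample size permits the second step. Evaluation of Pilot RCT Analysis names three prognostic factors as examples: education, psychiatric diagnosis severity and substance use.

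**The concern.** The protocol makes statistical significance the condition for entering a predictor and then refits the survivors on the same drop-outs. With few events this does two kinds of harm. A modest real predictor usually fails the screen, so its absence from the model says little. One that passes does so largely because its estimate happened to be high, and refitting it on the same data does not remove that excess. Characteristics with no link to drop-out can also pass by chance, more often as more are tested.

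Section D says that the feasibility results are meant to help plan a larger study, and section I.2 names a full-scale trial to follow. A chance or inflated predictor of drop-out could mislead that planning, for example in how retention effort is directed.

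**Working it through.** The protocol gives no drop-out count or power figure for this analysis, so there is no stated result to reproduce. The check builds on its inputs.

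**Inputs from the protocol**
- Randomised: 96 (G.1: "In order to successfully recruit the 96 AWARE participants"), equally allocated (F.4, step 7: "assign 48 to the AWARE intervention group and 48 to the wait-list group").
- Drop-out: 15% by 8 weeks and another 5% at 3 months (G.3).
- Level: 0.05 for every test, taken here as two-sided because the attrition tests do not state sidedness.

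**Assumptions**
- Number of characteristics: 3 to 20.
- Correlation between characteristics: 0 to 0.5.
- True difference for illustration: 0.3 SD on a continuous characteristic.

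**1. Number of drop-outs**
- 8 weeks: 96 × 0.15 = 14.4, about 14 against 82 retained.
- 3 months: 96 × 0.20 = 19.2, about 19 against 77. If the 5% applies to those remaining, 96 × (1 − 0.85 × 0.95) = 18.5.
- Per arm, if drop-out is equal: 48 × 0.15 = 7.2 and 48 × 0.20 = 9.6.

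**2. Smallest observed difference that passes the pooled screen**

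In SD units this is t(0.975, 94 df) × √(1/n₁ + 1/n₂), with t = 1.986.
- 14 against 82: 1.986 × 0.289 = 0.57 SD.
- 19 against 77: 1.986 × 0.256 = 0.51 SD.

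Any characteristic that passes therefore shows at least 0.51 to 0.57 SD, whatever its true size.

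**3. Fate of a true 0.3 SD predictor** (power from the noncentral t distribution; mean size when selected from simulated t tests)

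| Time point | Chance of passing | Mean size when it passes | Overstatement |
|---|---|---|---|
| 8 weeks (14 vs 82) | 18% | 0.73 SD | 2.4 times |
| 3 months (19 vs 77) | 21% | 0.66 SD | 2.2 times |

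A true 0.5 SD predictor passes 40% (8 weeks) to 49% (3 months) of the time and is overstated 1.6 and 1.4 times respectively. For a binary characteristic with 50% prevalence (assumed) and a true odds ratio of 2, the chance of passing is 21% to 26%, and the average odds ratio when it passes is about 4.8 and 4.0.

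**4. Chance of at least one false predictor at one time point**

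For k independent tests this is 1 − 0.95^k. The second column assumes a common correlation of 0.5.

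| k | Independent | Correlation 0.5 |
|---|---|---|
| 3 | 14% | 13% |
| 10 | 40% | 29% |
| 20 | 64% | 42% |

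Over both time points together, with the 8-week drop-outs counted again at 3 months, ten characteristics give about 49% (correlation 0.3) to 54% (independent).

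**5. Events per predictor in a by-group model, if it is fitted as one model per arm**
- 8 weeks: 7.2/2 = 3.6 events for each of two predictors; 7.2/3 = 2.4 for each of three.
- 3 months: 9.6/2 = 4.8 and 9.6/3 = 3.2.

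Even one predictor would have only about 7 to 10 events. Under a rule of thumb of ten events per predictor (an assumption, not in the protocol), the pooled sample supports one predictor and a single arm supports none.

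**The case against.** The strongest reply is proportionality. This is a pilot without a formal sample-size calculation, no hypothesis concerns predictors of attrition, and the enrolment and adherence proportions, which matter more for planning, are estimated with 95% confidence intervals. The covariate list and the threshold for sample size could properly sit in a statistical analysis plan. All of this stands, and it keeps the point minor. It does not remove it: the protocol itself chooses significance as the entry rule, and a covariate list elsewhere would not undo the effect of that rule.

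Low power also comes from the few drop-outs, and no rewording cures that. Confidence intervals would show the imprecision, where a significance screen hides it.

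Several stronger readings are tempting but not supported:
- A reader might infer that a by-group model will certainly be fitted. The text makes it conditional on sample size, and at 7 to 10 drop-outs per arm it may never be run. The phrase *by group* may also not mean separate models per arm.
- A reader might infer that the screening itself is done within arms. It is pooled, so 14 against 82 and 19 against 77 are the comparisons that govern.
- A reader might infer that only significant associations will be reported. The protocol says that the bivariate associations will be examined. Significance governs entry to the model, and nothing restricts reporting.
- A reader might infer that these predictors will determine the design of the next trial. Section D speaks only of better planning in general, and no design decision is tied to them.
- A reader might infer that false predictors are likely whatever is tested. With only the three factors named as examples, the chance is about 13% to 14% per time point.

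**Conclusion.** The concern holds as a minor weakness in an exploratory analysis. The firmest part does not depend on how many characteristics are tested: at the protocol's own drop-out rates, the screen would miss a true 0.3 SD predictor about four times in five and overstate it more than twofold when it passed. This rests on the anticipated 15% and 5% losses, two-sided tests, and 0.3 SD as an illustrative effect; larger true effects suffer less.

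The false-positive rate is less certain, because it follows from an unstated number of tests. The problem with the by-group model arises only if that model is fitted. The results could mislead planning of the larger study, but the analysis feeds no efficacy or safety conclusion.

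**What to change.** In G.3, Aim 2, part (1), remove bivariate significance as the condition for entering the model. Report the association of every examined baseline characteristic with attrition, at each time point, as an estimate with a 95% confidence interval, labelled exploratory.

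If a model is wanted, replace the by-group models with one pooled model per time point, containing arm and one or two predictors named in advance. Psychiatric severity and substance use are natural candidates, since the protocol already names them as prognostic factors. A small-sample method such as Firth-penalised logistic regression would suit the event counts. The same sentence should also settle on one outcome, since it now moves between adherence and attrition.

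The cost is the rewording of two sentences, with no new data. The downside is that characteristics not named in advance can only be described, not put forward as predictors.
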